8.2 Derived Variables

The following sections provide a general description of the derived variables for data analyses.

8.2.1 Reference Dates

Reference date for Treatment Period 1 is first infusion date of Week 1 Visit. Reference date for Treatment Period 2 is the first infusion date of Week 17 Visit.

8.2.2 Study Day

If the date of interest occurs on or after the reference date for Treatment Period 1 then the study day will be calculated as (date of interest - reference date for Treatment Period 1) + 1. If the date of interest occurs before the reference date of Treatment Period 1 then the study day will be calculated as (date of interest – reference date for Treatment Period 1). There is no study day 0.

8.2.3 Time to Event Variables and Durations

The following durations are calculated:

- Time to onset of AE from start of last infusion prior to onset of AE (minutes)

$$\text{Time to onset of AE from start of last infusion time} = \frac{(\text{start date/time of AE} - \text{start date/time of most recent infusion})}{60}$$

If the start time of an AE is missing, the time to onset of AE from last infusion will be missing.

- Time to onset of AE from start of corresponding Treatment Period (days)

$$\text{Time to onset of AE from start of corresponding Treatment Period} = \text{start date of AE} - \text{start date of first infusion of Treatment Period} + 1$$

- Duration of AE (minutes)

$$\text{Duration of AE} = (\text{end date/time of AE} - \text{start date/time of AE})$$

If the start time or the end time of the AE is missing, the duration of the AE will be missing.

- Duration of Exposure (days)

$$\text{Duration of Exposure (Overall)} = \text{start date of first IP infusion} - \text{end date of last IP infusion} + 1$$

$$\text{Duration of Exposure (IgPro10)} = \text{start date of first infusion of IgPro10} - \text{end date of last infusion of IgPro10} + 1$$

$$\text{Duration of Exposure (IgPro20)} = \text{start date of first infusion of IgPro20} - \text{end date of last infusion of IgPro20} + 1$$

- Duration since *SSc history event* (months)

$$\text{Duration} = (\text{start date of first IP infusion} - \text{imputed date of } SSc \text{ history event}) / 30.4375$$

where *SSc history event* is Date of Diagnosis of SSc, Date of first Raynaud's phenomenon, and Date of first non-Raynaud's phenomenon.

If only the year of the event date is reported, the event date will be imputed by July, 1st of that year. If only year and month of the event date is reported, the event date will be imputed by the 15th of that month.

When reporting durations in months, the number of days will be divided by 30.4375; to report in weeks the number of days will be divided by 7; to report in years the number of days will be divided by 365.25.

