2.1.2 Primary Endpoints

The primary endpoint of the study is the safety of IgPro20 based on:

Safety Endpoints	Summary Measure
AEs, including any AEs, treatment-emergent adverse events (TEAEs), serious adverse events (SAEs), and adverse events of special interest (AESIs)	
AEs measured by treatment, treatment sequence, combination of treatment, and treatment period (Period 1, Week 16; Period 2, Week 32; combination of treatment, Week 32):
 
 Number and percentage of subjects with AEs, TEAEs, SAEs, and AESIs (total, severity, causality, and outcome) Number and percentage of subjects with AEs categorized as ISRs (total, severity, causality and outcome) Rate of ISRs per subject and per infusion Onset and duration of ISRs
Change in other clinical tests	
Changes from baseline as measured by treatment, treatment sequence, combination of treatment and treatment period:
 
 Vital signs Body weight Clinical laboratory tests Electrocardiogram (ECG) Pulmonary function tests (PFTs)

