8.1.1.10 Patient Diary

Subjects will receive a patient diary at each site visit during the IgPro20 sequence and will be instructed to record any side effects that occur between site visits, including start and stop dates. Subjects will return the diary at the next site visit and receive a new diary. Investigators will review the diaries and determine if any of the side effects qualify as AEs.

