10.3.2 Analyses of Primary Endpoints

10.3.2.1 Safety of IgPro20

Safety data collected while subjects are treated with IgPro20 will be summarized by treatment sequence. All AEs will be coded by the Medical Dictionary for Regulatory Activities in System Organ Class and Preferred Term. Treatment-emergent adverse events, defined as AEs reported at or after the start of the first infusion in the study, will be summarized in number and percentages by treatment sequence. Summaries of TEAEs by

severity, causal relationship, seriousness, and leading to interruption and / or withdrawal will be provided.

Infusion site reactions will also be summarized separately following the analyses for all TEAEs. Additional summary statistics including 95% CIs will be presented for rate of ISRs per subject and per infusion. Descriptive statistics of time to onset and duration of ISRs will be presented. Detailed information about ISRs related to infusion sites will be provided.

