2.0	09 Nov 2021	PPD	
 • Minor editorial changes • Signature page adapted to new electronic signature process • Major PD -> Key PD • Section 3: Document versions updated • Glossary: Infusion terminology clarified. • Section 4.6/ 5: Interim Analysis: Changed timing and purpose (change from CSP), specification added • Section 6: SAF-IgPro10 and SAF-IgPro20 added • Section 6: PP-IgPro10 and PP-IgPro20 added, PK analysis set removed • Section 7.4 (COVID-19 Impact) added • Section 8.1.2: Imputation rules for Concomitant Medication changed • Section 8.2.3: Duration of AE and Time to Onset from last infusion is expressed in minutes • Section 8.2.3: Duration since SSc history event added • Section 8.2.9 and 10.1: CCI response added • Section 8.2.13: 'Other aids' can now be assigned to an activity • Section 8.2.13: Screenshots for CCI CCI added • Section 8.3.2: Categorization of Concomitant Medications takes now start and end times into account • Section 8.4.2: Deleted "two consecutive visits" for vital signs and CCI • Section 9: Clarification of handling of re-screened subjects • Section 9.1: List of parameters re-arranged • Section 9.3: Auto-antibodies at baseline added • Section 9.3/9.4: Summaries for background therapy/ immunosuppressants at baseline added

Ver- sion	Effective Date	Author of Modification	Reason for Change

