End Date	any date element	No imputation for completely or partially missing AE end dates; the AE duration will be set to missing.

Medical History

End dates of Medical History are used to differentiate between past and current medical condition. If a partial end date is possibly after first IP intake the MH will be considered concomitant.

Date	Missing Element	Rule
Start Date	any date element	No imputation for completely or partially missing start dates
End Date	day, month, and year	Do not impute completely missing MH end dates. The MH will be deemed “concomitant”.
	day, month only	Set the end date to December 31.
	day only	Set the end date to the end of the month.

Concomitant Medication

Start and end dates will be imputed for use to derive the reference variables for concomitant medication start and end relative to treatment; any imputed dates will be included in analysis datasets with an identifier as imputed. The reference variables will be used to differentiate before, during and after treatment for the concomitant medication.

In general, an incomplete CM start date will be imputed such that the medication starts as early as possible after the first IP infusion, irrespective of actual treatment.

Date	Missing Element	Rule
Start Date	day, month, and year	Do not impute completely missing concomitant medication start dates; all values that depend on this date will be set to missing
	day, month only	
 If the study treatment start date is not missing: 
 If the year of CM start date is the same as the year of study treatment start date 
 If the CM end date indicates the CM ended prior to study treatment start date then set CM month and day to January 1 Otherwise set month and day of CM start date to study treatment start date If the study treatment start date is missing then set month and day of CM start date to January 1.

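### The SAP's rules for ISR duration lose usable data (reactions with both dates known but no clock time, and all reactions without an end date), and the printed minutes formula lacks its unit conversion

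*SAP*

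**What the plan says.** Protocol 2.1.2 lists "Onset and duration of ISRs" among the primary endpoint measures, and SAP 4.2 repeats it. Protocol 10.3.2.1 plans a descriptive analysis only: "Descriptive statistics of time to onset and duration of ISRs will be presented". SAP 11.2 includes duration of ISR among the additional summaries for the IgPro20 periods.

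The derivation is in SAP 8.2.3. The version 2.0 entry in the SAP's modification history gives the intended unit: "Duration of AE and Time to Onset from last infusion is expressed in minutes". The onset formula divides a date/time difference by 60. The duration formula is end date/time minus start date/time, with no divisor.

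Two rules set duration to missing. For clock times, SAP 8.2.3 states: "If the start time or the end time of the AE is missing, the duration of the AE will be missing". For end dates, SAP 8.1.2 states: "No imputation for completely or partially missing AE end dates; the AE duration will be set to missing".

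On data capture, Protocol 8.1.1.10 tells subjects in the IgPro20 period to "record any side effects that occur between site visits, including start and stop dates". Clock times are not mentioned.

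**The concern.** The trial studies a subcutaneous product in a disease of skin and small vessels. Protocol 1.1 gives that pathology as the reason for a separate safety study, and Protocol 1.4.1.1 names ulceration-like ISRs as an important identified risk. How long reactions last, including those that do not resolve, is therefore a central descriptive result.

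The rules as written exclude two groups from the duration summary. The first is ISRs with both dates known but a clock time missing; a duration in days could be computed for these and is discarded. The second is ISRs with no end date, which includes those still unresolved. If unresolved reactions are the long ones, the summary describes only the shorter part of the distribution.

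The missing divisor is a separate matter. Two variables declared in the same unit, in the same section, have formulas that cannot both be literal code on the same time scale.

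**Working it through.** The documents give no figure for ISR duration, so there is none to reproduce. The check has three parts.

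**1. Unit.** Inputs: the two formulas in SAP 8.2.3 and the declared unit, minutes. The divisor of 60 in the onset formula implies differences held in seconds. For a reaction lasting 24 hours:

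- Difference in seconds: 24 × 60 × 60 = 86,400.
- With the divisor used for onset: 86,400 / 60 = 1,440 minutes.
- Duration formula coded literally on the same scale: 86,400, which is 86,400 / 1,440 = 60 times too large.

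An error of this kind would lengthen durations.

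**2. ISRs without an end date.** Input: the end-date rule in SAP 8.1.2. The distribution is an assumption, not taken from the documents: log-normal with median 24 h and log-SD 1.0 or 1.5 (400,000 simulated values). The longest share u is taken to be unresolved and is dropped.

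| u dropped | Mean, log-SD 1.0 (all: 39.4 h) | Median (all: 24.0 h) | Mean, log-SD 1.5 (all: 73.7 h) | Median (all: 24.0 h) |
|---|---|---|---|---|
| 2% | 34.3 | 23.4 | 53.6 | 23.2 |
| 5% | 30.7 | 22.5 | 43.4 | 21.9 |
| 10% | 26.7 | 21.1 | 34.0 | 20.0 |
| 20% | 21.6 | 18.6 | 23.6 | 16.5 |

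A hand check of one cell: after dropping the top 20%, the median of the rest is the 40th percentile of the whole, 24 × exp(1.0 × (−0.253)) = 18.6 h.

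For scale, Protocol 10.1 plans 20 × 28 = 560 infusions and expects an ISR rate of 0.1 to at most 0.5, so 56 to 280 ISRs. At 56 ISRs, 2% to 20% is about 1 to 11 reactions.

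**3. ISRs without a clock time.** Same assumed distribution, log-SD 1.0 (all reactions: mean 39.4 h, median 24.0 h). The probability that a time is missing differs for reactions up to and beyond 24 h.

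| Missing if ≤ 24 h | Missing if > 24 h | Mean kept (h) | Median kept (h) |
|---|---|---|---|
| 30% | 30% | 39.4 | 24.0 |
| 10% | 50% | 31.7 | 18.1 |
| 50% | 10% | 47.1 | 31.8 |

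The summary can be unbiased, too short or too long. Information is lost in every case.

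The SAP does allow for missing AE times elsewhere. SAP 8.3.1 classifies an event as treatment-emergent by date when the time is absent. SAP 11.2 assigns temporal association by calendar day, up to three days after the infusion. Duration has no equivalent fallback.

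**The case against.** A reader might infer that ISR duration will be both mis-scaled and biased short. The documents do not support that, for several reasons.

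- **Scale.** The unit is declared as minutes, and end minus start expressed in minutes is correct. SAP 11.1 writes infusion duration in just that way. SAP 8.2.3 also prints duration of exposure as start minus end plus 1, which is zero or negative for any exposure beyond one day, so its formulas are evidently not literal code. This stands: the factor of 60 is conditional, and it would act in the opposite direction to a short bias.
- **Home infusions.** Up to 7 + 12 + 2 = 21 of 28 IgPro20 sessions (75%) take place at home, which might be read as the share depending on the diary. It is not. A nurse gives those infusions and AEs are recorded at the visits. Late reactions after a site infusion also go to the diary. The second session in odd weeks only may be at home, so 21 is a maximum. This stands.
- **Clock times.** Asking for dates does not exclude times. The investigator reviews the diary and AEs are entered on the eCRF, which is not among the documents. This stands, so neither the share lost nor the direction can be stated.
- **Unresolved ISRs.** The protocol expects ISRs to resolve quickly, and follow-up after the last IgPro20 week runs about 36 − 14 = 22 weeks in Sequence A and 36 − 30 = 6 weeks in Sequence B. Such ISRs stay in the counts, the outcome summary and the listing, and n is reported. This limits the harm but does not remove it: neither n nor the outcome table corrects the duration estimate or says why values are missing.
- **Kaplan-Meier.** ISRs cluster within subjects, which is the SAP's own reason for dropping the per-infusion confidence interval. This stands against a naive interval, not against a descriptive median.

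**Conclusion.** The concern holds in a limited form. As written, the rules discard ISRs whose dates are both known and give no duration to ISRs without an end date, for a listed primary endpoint measure. Dropping unresolved ISRs shortens the summary where those are the longest reactions. In the illustration the mean falls by 5.1 to 17.8 h (39.4 to 34.3 or 21.6 h) at log-SD 1.0, and the median by 0.6 to 5.4 h. These sizes rest on the assumed log-normal shape, the 24 h median and the 2% to 20% range, none of which is in the documents.

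The direction of bias from missing clock times is not established. Longer reactions may well lack times more often given the diary wording, but this cannot be confirmed without the eCRF. The missing divisor is a textual inconsistency that becomes a 60-fold error only if the formula is coded literally in seconds.

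The analysis is descriptive and no hypothesis is tested, so the point is worth correcting before the tables are programmed but does not threaten the trial's main conclusions.

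**What to change.** In SAP 8.2.3, 8.1.2 and 11.2:

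1. Print the conversion to minutes in the duration formula, consistent with the onset formula.
2. Report ISR duration in days (end date − start date + 1) for all ISRs with both dates known, with minutes as a supplement where both clock times exist.
3. Treat ongoing ISRs as censored at last follow-up and give a descriptive Kaplan-Meier median in days. Give no confidence interval that treats ISRs as independent. The SAP should name the censoring date, because Protocol 9.5 ends follow-up of non-serious AEs at study completion while Protocol 9.6.1 continues beyond the EOS visit.
4. Report the number of ISRs ongoing and the number with missing duration, by reason (no clock time, partial or missing date).

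The cost is SAP wording and minor programming, with no new data collection. The drawback is coarser resolution: a ten-minute same-day reaction counts as one day in the days summary, which is why the minutes summary should be kept beside it.

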8.2.4 Baseline Definition

Baseline is defined as the most recent, non-missing value prior to the start date and time of the first study treatment infusion. Results from unscheduled visits will be taken into account.

If date is given for an assessment only and the time is missing, and the date of the assessment is the same as the date of the first study treatment infusion then this assessment is NOT considered baseline.

8.2.5 Change from Baseline or Reference Visit

Change from baseline will only be calculated for measures that have post-baseline records. Change from baseline is calculated as:

- Change from baseline = visit value – baseline value.

Percentage change from baseline is calculated as:

- Percentage change from baseline = $100 * \text{change from baseline} / \text{baseline value}$

If either the baseline or visit value is missing, the change from baseline and percentage change from baseline is set to missing as well.

The change from reference visit will be calculated following the same rules.

8.2.6 Multiple Assessments

All data will be reported according to the nominal visit date for which it was reported (that is, no visit windows will be applied during data set creation to re-assign assessments to other visits or time points based on such windows).

Data from all assessments (scheduled and unscheduled), including multiple assessments, will be included in listings.

8.2.7 Actual Treatment

The subjects' actual treatment will be derived from exposure data delivered by IRT. If a subject receives study treatment that is the same as the assigned treatment, then actual treatment is the assigned treatment. If a subject receives study treatment that is different from the assigned treatment for the entire time of a Treatment Period, then actual treatment is the different treatment (the treatment actually received).

8.2.8 Body Mass Index (BMI)

BMI will be calculated using the following formula:

$$\text{BMI (kg/m}^2\text{)} = \text{Weight (kg)} / [\text{Height (m)}]^2$$

using the height measured at Screening and the weight measured at Week 1. If weight at Week 1 is not available, the assessment at Screening will be used. If neither is available, then BMI is missing.

[figure not shown]
8.2.9

CCI

CCI

[figure not shown]

CCI

[figure not shown]
8.2.10 CCI

CCI

[figure not shown]
8.2.11 CCI

CCI

8.2.12 CCI

CCI

CCI

[figure not shown]
8.2.13 CCI

CCI

Figure 2: **CCI**

CCI

CCI

[figure not shown]
[figure not shown]

Figure 3: CCI

CCI

CCI

8.2.14 CCI

CCI

CCI

8.2.15 CCI

CCI

CCI

Figure 4: CCI

CCI

[figure not shown]
CCI

CCI

CCI

8.2.16 CCI

CCI

[figure not shown]
[figure not shown]

Figure 5: CCI [Redacted]

8.2.17 CCI [Redacted]

CCI [Redacted]

CCI [Redacted]

8.2.18 CCI [Redacted]

CCI [Redacted]

8.2.19 CCI [Redacted]

CCI [Redacted]

8.2.20 CCI [Redacted]

CCI [Redacted]

8.2.21 CCI [Redacted]

CCI [Redacted]

Figure 6: CCI

CCI

8.3 Study Periods Relative to Treatment

Definitions of the endpoint assessment and definition of start and end of study periods are presented in [Table 1](#) and [Table 2](#).

Table 1: Timing of Endpoint and Reference Assessments

	Definition	Start of Assessment Period	End of Assessment Period
By Treatment	1 IgPro20 Treatment Sequence A/ Treatment Period 1 and Treatment Sequence B/ Treatment Period 2	Week 1 Week 17	Week 17 ¹ Week 32
	2 IgPro10 Treatment Sequence A/ Treatment Period 2 and Treatment Sequence B/ Treatment Period 1	Week 17 Week 1	Week 32 Week 17 ²
By Treatment Sequence	1 Treatment Sequence A	Week 1	Week 32
	2 Treatment Sequence B	Week 1	Week 32
By Treatment and Treatment Period	1 IgPro20 in Treatment Period 1 Treatment Sequence A	Week 1	Week 17 ¹
	2 IgPro10 in Treatment Period 1 Treatment Sequence B	Week 1	Week 17 ²
	3 IgPro10 in Treatment Period 2 Treatment Sequence A	Week 17	Week 32
	4 IgPro20 in Treatment Period 2 Treatment Sequence B	Week 17	Week 32
Overall	1 Both Treatment Sequences, all Treatment Periods Treatment Sequence A/ Treatment Period 1, Treatment Sequence B/ Treatment Period 1, Treatment Sequence A/ Treatment Period 2, Treatment Sequence B/ Treatment Period 2	Week 1 Week 17	Week 17 Week 32

¹ Before first infusion of IgPro10.² Before first infusion of IgPro20.

Table 2: Treatment Periods

Treatment Sequence/ Treatment Period	Treatment	Start of Treatment Period	End of Treatment Period
Treatment Sequence A/ Treatment Period 1	IgPro20	Start date and time of the first IgPro20 Infusion	Start date and time of the first IgPro10 Infusion or EOS, if there is no IgPro10 Infusion
Treatment Sequence A/ Treatment Period 2	IgPro10	Start date and time of the first IgPro10 Infusion	EOS
Treatment Sequence B/ Treatment Period 1	IgPro10	Start date and time of the first IgPro10 Infusion	Start date and time of the first IgPro20 Infusion or EOS, if there is no IgPro20 Infusion
Treatment Sequence B/ Treatment Period 2	IgPro20	Start date and time of the first IgPro20 Infusion	EOS

8.3.1 Study Periods for Adverse Events

AEs with onset date/ time at or after start of first infusion of study treatment are TEAEs. If the time of onset of an AE is missing: AEs with onset date at or after start of first infusion of study treatment are TEAEs. Assessment whether an AE is considered treatment-emergent, will take place after imputation of partially missing dates (see [Section 8.1.2](#)).

The TEAE analysis will be done for the study periods and groups shown in [Section 11](#). An AE will be counted for the analysis of a study period if the onset of the event falls within the study period. For the definition of start and end of the study periods see [Table 2](#).

